In anticipation of this protocol, we have pilot-tested the curriculum at three affiliated institutions with general surgery residents at varying levels of training. Focus group data was collected to garner feedback on the effectiveness and feasibility of the curriculum. **The purpose of the current protocol is to implement the curriculum across eight institutions and measure resident-level competency outcomes, as well as patient-reported and clinical outcomes, following this training.**

RESEARCH DESIGN AND METHODS

Briefly describe study design and anticipated enrollment, i.e., number of subjects to be enrolled by researchers study-wide and by Partners researchers. Provide a brief summary of the eligibility criteria (for example, age range, gender, medical condition). Include any local site restrictions, for example, "Enrollment at Partners will be limited to adults although the sponsor's protocol is open to both children and adults."

We will conduct a cross-over, cluster-randomized trial at 8 academic medical centers (AMCs) to capture the effect of PACTS on: 1) resident knowledge and attitudes regarding cross-cultural health care [Specific Aim (SA)1], 2) interpersonal and communication skills in simulated patient-clinician encounters [SA2], and 3) patient-reported satisfaction with resident physicians involved in their care, and clinical outcomes [SA3]. Sites will be assigned to an early intervention/retention assessment group or a control group with delayed intervention for examination of the effectiveness of the intervention as well as learner retention. After cluster-randomization, we will assess the residents' knowledge, attitudes, and skills prior to and after the PACTS curriculum at half the sites (Early Intervention/Retention Group). We plan to conduct follow-up testing after one year to evaluate learner retention.

At the other sites (Delayed Intervention Group), we will conduct baseline testing prior to the standard residency curriculum, and administer the PACTS curriculum the following year. This study design will enable us to examine both between- and within-group differences based on curriculum exposure in intervention year 1 as well as within-group differences for the Delayed Intervention Group at the end of year 2. Further, we will also be able to test post-exposure effect retention in the Early Intervention Group at the end of year 2.

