We are partnering with eight general surgery residency programs and their affiliated hospitals to conduct the PACTS Trial. Programs have been matched to achieve balanced cohorts in terms of program size and diversity of patient population. Based on case mix, we anticipate approximately 40% of the patient population in this study will be of minority descent. The eight programs that will be participating in this study are: 1) Johns Hopkins University, 2) Brigham and Women's Hospital, 3) Brown University, 4) Eastern Virginia Medical School, 5) Massachusetts General Hospital, 6) Beth Israel Deaconess Medical Center, 7) Howard University, and 8) Washington University in St. Louis.

Briefly describe study procedures. Include any local site restrictions, for example, "Subjects enrolled at Partners will not participate in the pharmacokinetic portion of the study." Describe study endpoints.

Surgery Focus Group

In anticipation of the implementation of the cross-over, cluster-randomized trial at the 8 academic medical centers, we hope to gather feedback from surgical residents, medical students, and surgical faculty in training programs outside of these sites to assist in the development of the cultural dexterity curriculum. We believe that surgical conferences would be the best opportunity to gain insight regarding the current curriculum content as well as curriculum implementation. Contributions from surgical residents, medical students, and surgical faculty will be important to supplement the previous input from surgical faculty and program directors.

We plan to recruit participants from the surgical specialty excluding those from our 8 academic medical centers. We will disseminate one of four modules of the curriculum in advance for review. Participants will then be scheduled for a 1 hour-long focus group based on their availability, with a total of four focus groups. Focus groups will be facilitated by two study staff in a semi-structured focus group model. We believe this input will be integral in ensuring that our cultural dexterity curriculum can eventually be implemented in all surgical training programs across the country.

Patients Focus Group

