Four populations of human subjects will be involved in this study: 1) surgical residents (clinical post-graduate years 1-5) from the 8 academic medical centers, 2) patients treated by those residents, 3) surgical residents outside of the 8 academic medical centers who will participate in focus groups and survey pilot, and 4) previous or current nonsurgical patients prior to the implementation of the PACTS curriculum who will participate in the patient focus group and patient survey pilots.

TARGETED/PLANNED ENROLLMENT: Resident subjects (n=400)			
Ethnic Category	Females	Males	Total
Hispanic or Latino	9	19	28
Not Hispanic or Latino	123	249	372

Ethnic Category: Total of All Subjects	132	268	400
Racial Categories			
American Indian/Alaska Native	1	3	4
Asian, Native Hawaiian, or Other Pacific Islander	25	51	76
Black or African American	8	16	20
Other	16	32	48
White	73	147	220
Racial Categories: Total of All Subjects	123	249	372

TARGETED/PLANNED ENROLLMENT: Patient subjects (n=2400)			
Ethnic Category	Females	Males	Total
Hispanic or Latino	300	300	600
Not Hispanic or Latino	900	900	1800
Ethnic Category: Total of All Subjects	1200	1200	2400
Racial Categories			
American Indian/Alaska Native	24	24	48
Asian, Native Hawaiian or Other Pacific Islander	120	120	240
Black or African American	300	300	600
White	456	456	912
Racial Categories: Total of All Subjects	900	900	1800

Surgical residents: All residents at each study site will receive the educational intervention. Enrollment and consent will be discussed by the research assistant, and program directors will not have access to resident enrollment information. We anticipate enrolling 400 surgical residents at the beginning of the study. We expect that the population will have the following racial composition based on average racial composition of surgical residency programs as reported by the Accreditation Council of Graduate Medical Education (ACGME): 55% White, 6% Black, 7% Hispanic, 19% Asian/Pacific Islander, <1% Native American, and 12% other.¹ They will range in age from 25 to 36. Based on the ACGME reports, approximately 33% of these residents will be female, and resident subjects will not be excluded from the study based on their gender.

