Patients: We will recruit 3,105 patients overall, and approximately 345 patients per site. To be included in the study, patient subjects must be admitted to a surgical service under the care of a resident enrolled in the study, able to recognize a photo of the resident as a main care provider, fluent in English, Spanish, Portuguese, Haitian Creole, Simplified Chinese, or Traditional Chinese, and older than 18 years of age. We will oversample

minority patients to achieve at least 40% Black and Hispanic patients. We will identify patients using the patient list from each resident enrolled in the study during the 2-month pre- and post- data collection windows. We are targeting underrepresented minority patients because they are at most risk for poor communication with providers and such interactions have greater potential for improvements.

White patients will not be excluded from the study; the emphasis is on racially discordant physician/patient dyads, and white patients will be included for the assessment of non-white resident subjects. As we expect that the gender demographics of the patient subject group will somewhat reflect the gender demographics of the general population, we anticipate 50% of the patient subjects to be female. There will be no exclusion of subjects based on gender or ethnicity.

Residents and patients will be recruited from 8 sites: Brigham and Women's Hospital, Beth Israel Deaconess Medical Center, Massachusetts General Hospital, Brown University, Howard University, Johns Hopkins University, Eastern Virginia Medical School, and Washington University in St. Louis. Each of these sites is in or near a major metropolitan area, with racially and ethnically diverse patient populations. Research assistants at each site will have access to each resident subject's panel of inpatients, which will also allow the research assistant to identify the patients' racial information and proximity to discharge from the hospital. For the Residents Curriculum Impact Focus Groups, the residents will be recruited from the residents already consented and enrolled in the trial. The PACTS Program/ Curriculum Evaluation will be provided to all residents who have undergone the curriculum.

Focus group participants outside of the 8 AMCs

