All general surgery residents will receive the educational curriculum; each site's Program Director (PD) has agreed to schedule PACTS training during compulsory didactic sessions, when residents are free from clinical duties. However, participation in study assessments (OSCEs and knowledge-testing) is voluntary and will not impact residents' performance in their program. Final analyses will include enrolled residents regardless of their attendance in live modules, reflecting an "intention-to-treat" analysis approach. This will more accurately demonstrate the "real world" benefit of PACTS, as not all residents may be able or willing to attend all live sessions. Based on the size of the residency programs, which ranges between 46 and 72 residents, and the away rotation schedules, we expect to enroll 200 residents per arm for analysis (an average of 50 residents per site).

Patient Recruitment

At the onset of clinical rotations, the Program Manager will contact surgical residency Program Coordinators to attain general surgery resident rotation schedules. The Program Manager will identify the dates and times of resident study participants' rotations. On these dates and times, Research Assistants working under the supervision of the Program Manager will verify that the resident is on rotation and use the EHR at the surgical service site to

randomly select at least two eligible patients from the EHR. First, the RA will approach the patients' nurse and ask whether the nurse might have a concern regarding the selected patients' cognitive status. If the nurse has no concerns, the nurse will be asked to introduce study staff to the patient. Staff will provide an information sheet, describe the study, and ask them to identify a resident participating in the PACTS trial who they recall interacting with. The RA will explain the study and provide the patient with a copy of the Patient Information Sheet and survey, which will be administered via tablet or laptop computer to access the survey in the Partners-hosted REDCap database. Completion of the English or Spanish language survey will indicate consent to participate in the study and the patient will be enrolled.

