If the nurse has a concern, the nurse will be asked to introduce the RA will approach the patient, and the RA will assess interest in the study, and administer a validated cognitive impairment screening tool (e.g. the Brief Confusion Assessment Method or the 4AT). If the patient is not interested in participating in the study or has a positive screen for cognitive impairment, the RA will not enroll the patient. If the patient does not screen positive, they will then be showed the picture of the resident for confirmation as above.

Please see the Patient Recruitment Flowchart in the attachments for an overview.

Patient inclusion criteria are: (1) admitted to surgical service under care of a participating resident; (2) able to recognize resident as a main care provider from a photo; (3) fluent in English, Spanish, Portuguese, Haitian Creole, Simplified Chinese, or Traditional Chinese. Patient exclusion criteria are: (1) admitted to Intensive Care; (2) mentally impaired and/or not oriented to person/time/ place.

In total, we will enroll 3105 patients across all sites (Table 7). If the patient is ineligible or unwilling to participate, another patient will be randomly selected from the e-mail list of patients. Patient sampling will be such that 40% of included patients will be racial or ethnic minorities. The overall proportion of racial/ethnic minority patients at each institution ranges from 24%-47% (excluding Howard University which has 90%), suggesting sufficient diversity across sites. Patient populations in surgical service will likely be even more diverse, as this includes both emergency surgery and trauma patients.

Provide details of remuneration, when applicable. Even when subjects may derive medical benefit from participation, it is often the case that extra hospital visits, meals at the hospital, parking fees or other inconveniences will result in additional out-of-pocket expenses related to

study participation. Investigators may wish to consider providing reimbursement for such expenses when funding is available

Not applicable.

For guidance, refer to the following Partners policies:

Recruitment of Research Subjects

[https://partnershealthcare-public.sharepoint.com/ClinicalResearch/Recruitment Of Research Subjects.pdf](https://partnershealthcare-public.sharepoint.com/ClinicalResearch/Recruitment%20Of%20Research%20Subjects.pdf)

Guidelines for Advertisements for Recruiting Subjects

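### The protocol's patient target does not reconcile: 3,105 overall, about 345 per site at 8 sites (2,760), and an enrolment table of 2,400

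*Protocol*

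**What the plan says.** The protocol's patients paragraph under Equitable Selection of Subjects sets the target: "We will recruit 3,105 patients overall, and approximately 345 patients per site". Patient Recruitment repeats the total: "In total, we will enroll 3105 patients across all sites".

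The number of sites is eight throughout. Research Design and Methods states "We will conduct a cross-over, cluster-randomized trial at 8 academic medical centers (AMCs" and introduces the named programs with "The eight programs that will be participating in this study are". Equitable Selection of Subjects says "Residents and patients will be recruited from 8 sites" and names all eight. Monitoring and Quality Assurance also counts eight centers.

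The planned-enrolment table in the same protocol is headed "TARGETED/PLANNED ENROLLMENT: Patient subjects (n=2400", and its ethnicity rows (600 and 1,800) add to that figure. The 2017 SAP, in its section on patient-reported satisfaction and NSQIP outcomes, has the same total: 100 patients per site per collection phase, 300 per site, 2,400 in all.

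**The concern.** A total, a per-site figure and a number of sites given in one section should multiply out, and these do not. The enrolment table a page earlier gives a third total.

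What is at stake is the quota that research assistants recruit to within the two-month collection windows. The documents support 300, 345 or about 388 per site, depending on which figure is taken as governing. The enrolment table put before the ethics committee describes 705 fewer patients than the text says will be enrolled. Without a single target, nobody can say whether recruitment was met, and the final report cannot set planned against actual enrolment.

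**Working it through.** **Inputs.** Overall 3,105 and about 345 per site (protocol, Equitable Selection of Subjects); 3,105 again (protocol, Patient Recruitment); 8 sites (protocol, several sections); table total 2,400 (protocol, planned-enrolment table); 100 per site per phase and 300 per site (SAP).

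**1. Reproducing the stated totals.**
- The 2,400 reproduces: 300 / 100 = 3 phases, and 8 × 3 × 100 = 2,400.
- The 3,105 does not: 8 × 345 = 2,760. The gap is 3,105 − 2,760 = 345, and 345 / 3,105 = 11.1%.
- 3,105 / 345 = 9.0 exactly.
- 3,105 / 8 = 388.1 per site, which is 43.1 above 345 (43.1 / 345 = 12.5%).

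**2. The candidate totals side by side** (three equal phases, as in the SAP).

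| Total | Per site (8 sites) | Per site per phase | Excess over 2,400 |
|---|---|---|---|
| 2,400 | 300 | 100 | – |
| 2,760 | 345 | 115 | 360 (15.0%) |
| 3,105 | 388.1 | 129.4 | 705 (29.4%) |

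Only 3,105 fails to give a whole number per site or per phase at eight sites. At nine sites it is 9 × 3 × 115.

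**3. Could a ninth site explain it?** None is documented. The resident target in Resident Recruitment ("we expect to enroll 200 residents per arm for analysis (an average of 50 residents per site") gives 2 × 200 = 400 = 8 × 50; nine sites would give 450.

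**4. Could an allowance explain it?** The only sample-loss figure is the SAP's 20%, which is for residents. Applied to 2,400 it gives 2,400 × 1.2 = 2,880 or 2,400 / 0.8 = 3,000, and neither matches 2,760 or 3,105. An unstated 15% uplift would link the per-site figures (300 × 1.15 = 345), but that still yields 2,760 at eight sites.

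**5. Does the selection rule settle it?** Research assistants are to "randomly select at least two eligible patients from the EHR" for a resident on rotation. If each of 50 residents per site is sampled once per phase (an assumption), that is a floor of 2 × 50 × 3 = 300 per site. The other totals need averages of 345 / 3 / 50 = 2.3 and 388.1 / 3 / 50 = 2.59 patients per resident per phase. A minimum of two permits all three and selects none.

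**6. Effect on the stated power.** With three equal phases and two equal arms, the totals give 400, 460 or 517 patients per arm per phase, and 800, 920 or 1,035 per phase with the arms pooled. All exceed Table 7's 361 (pain satisfaction) and 377 (readmissions). At the smallest, 400 per arm, a simple two-proportion calculation gives 86% power for 63% against 73% and 82% for 23% against 15%. This ignores clustering, as Table 7 does.

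**The case against.** The best reply is that the target is inconsistent, not absent. The protocol's narrative gives one total, twice, and one per-site quota, so a research assistant reading it finds 345. The 300 per site is written only in the older SAP, and 388 is written nowhere. That is fair, but the 345 does not deliver the total printed beside it, and the protocol's own table corresponds to 300.

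A second reply is that the resident arithmetic cannot show how the patient total was produced. Because 3,105 is exactly nine quotas, a nine-unit multiplier is a plausible source of the slip. This also stands as far as it goes: the origin of 3,105 is not stated, and what can be said is that no ninth site is documented. Similarly, a residents' attrition allowance has little bearing on patients, whom the SAP treats as independent samples. The check shows only that the one stated allowance does not close the gap. The patients-per-resident averages rest on an assumed sampling pattern and are not themselves evidence of a defect.

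Two possible defences fail. The word approximately does not stretch to a 12.5% difference. Nor is this just an older SAP lagging behind a newer protocol, since all three totals arise within the 2020 protocol itself.

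**Conclusion.** The concern holds. At eight sites the stated quota yields 2,760, which is 345 short of the stated 3,105, and the protocol's enrolment table has 2,400. The documents do not show which total is intended.

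The consequence is limited. Table 7's stated power is unaffected, given equal phases and arms and the SAP's unclustered method. No minority shortfall follows either: the 40% minimum is a percentage, and the enrolment table gives (600 + 600) / 2,400 = 50.0% Black and Hispanic patients, adding its Hispanic ethnicity row to its Black race row. This is a certain error in a stated sample size, modest in effect and cheap to correct; it should be corrected.

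**What to change.** State one patient target as sites × phases × patients per site per phase, choosing explicitly among:

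- **2,400:** 8 × 3 × 100, 300 per site;
- **2,760:** 8 × 3 × 115, 345 per site;
- **3,105:** about 388 per site at eight sites, or 9 × 3 × 115 if a ninth site exists and is documented.

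If the total includes a patient allowance, give its size and reason. Carry the chosen figure through the patients paragraph, Patient Recruitment, the planned-enrolment table (with its demographic rows rebuilt on that total) and the SAP's patient-outcomes section. Patient Recruitment cites a Table 7 for 3,105. The SAP's Table 7 does not contain that number, and the cited table may be in material not supplied, so this is not counted as an error; whichever table is meant should show the chosen total. Table 7's per-group minimums need no change on this account.

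The cost is a text and table correction in the protocol, and in the SAP if the total is not 2,400. Restating 2,400 or 2,760 adds no patients, though 2,400 also means lowering the stated quota from 345 to 300. Keeping 3,105 at eight sites means about 43 more patients per site than the protocol now states.

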Cover Page for ClinicalTrials.gov

Official Study Title:

Evaluation of a Cultural Dexterity Training Program for Surgeons: The PACTS Trial

NCT Number:

NCT03576495

Document:

Statistical Analysis Plan

Document Date:

June 6, 2017

PACTS ANALYSIS PLAN: The multi-year cluster-randomized study design will enable us to examine differences between and within the Early Intervention and Control/Delayed PACTS training groups across three unique time points (Year 2 pre-intervention, Year 2 post-intervention and Year 3 post-intervention). Details of statistical measures/methods and power calculations appear below.

Within-group differences (repeated measures).

Repeated measure differences on dichotomous outcomes will be examined using Chi-square and Fisher's exact tests, as well as unadjusted logistic regression models controlling for resident-specific demographic factors (e.g. age, IAT, post-graduate year, and sex).

Differences in ordinal outcomes (e.g. three- or five-point Likert scale reporting or ordered category scores) between pre- and post-intervention testing will be examined using Chi-square tests, unadjusted ordered logistic regression, and ordered logistic regression adjusted for resident- and program-specific factors. Table 7 depicts our sample size/power calculations, according to which we will be able to detect an 11% absolute difference in the proportion achieving "adequate" vs. "sub-optimal" dichotomized assessments before and after PACTS training. This accounts for an up to 20% sample loss from the expected 200 enrolled residents per group.

Between-group differences (independent measures). Pre- vs. post- differences in both self-reported and observer-assessed ordinal outcomes between the Early and Delayed Intervention groups will be assessed at the end of the first training period using Chi-square tests and unadjusted ordered logistic regression, as well as ordered logistic regression models controlling for resident- and program-specific factors. Previous work demonstrated that exposure to training similar to PACTS was associated with a 20-25% increase in the proportion of trainees achieving "adequate" scores on an OSCE-based assessment. Based on the number of residents in each arm (n=200), we anticipate that we will be able to detect a much smaller between-group difference even with up to 20% sample attrition over time (Table 7).

Pre- and post-intervention patient-reported satisfaction and NSQIP outcomes. Management of pain will be assessed using elements of the Pain Treatment Satisfaction Scale (PTSS).¹⁴⁰ Previous work by Gupta et al suggests that, on average, 63% of patients provided assessments of pain control satisfaction in the upper quintile of a standardized 10-point satisfaction scale.¹⁴¹ Subsequent to the intervention, it is estimated that 73% of patients treated by PACTS-trained residents will report satisfaction in the uppermost PTSS quintile. We expect an 8% decrease in readmissions, from 23% to 15% post-intervention. Pre-post intervention differences in patient-reported satisfaction and NSQIP outcomes will be assessed using Chi-square, Fisher's exact tests, or t-tests as appropriate, and ordinal scale differences will be assessed using Chi-Square tests and ordered logistic regression, both without adjustment and controlled for patient-, clinician-, and facility-level factors. It is important to note that the patient groups represent independent samples, and these pre- and post-intervention measures are independent measures, not repeated measures (Table 8). To achieve this, we will recruit 100 patients per site for each data collection phase. Thus, we will collect 300 patients per site over the entire study (2,400 total), giving ample power for both patient and clinical outcomes.

Table 7. Sample Size Calculations

Example Measure	Proportional Difference to be Measured	Expected Minimum Number of Participants Per Group	Minimum Detectable Difference (80% power and $\alpha=0.05$)
Sample size/power calculations for repeated measures			
Within group resident knowledge/skills/attitudes	Pre- vs. Post-test proportion achieving "Adequate" vs. "sub-optimal" dichotomized assessments	Pre-intervention: 160 Post-intervention: 160 (Repeated Measures)	Pre-intervention: 50.0% Post-intervention: 61.0% Thus, we expect to be able to detect a proportional absolute difference of 11% for within-group assessments.
Sample size/power calculations for independent measures.			
Between group resident knowledge/ Skills/attitudes	Post-test proportion in Early Group vs. Delayed Group achieving "adequate" vs. "sub-optimal" dichotomized assessments	Early Group: 159 Delayed Group: 159 (Independent Measures)	Change from 50% to 65.5% Assuming remains at 50% with no change from baseline assessment. Thus, we would be able to detect a 15% relative proportional difference between groups associated with exposure to PACTS training.
Patient-reported within and between-group differences			
Patient-reported outcomes	Pre- vs. Post-test proportion of patients reporting pain-satisfaction scores in the uppermost standardized quintile	Pre-intervention: 361 Post-intervention: 361 (Independent Measures)	Proportion of Patients with scores Pre-intervention: 63.0% Post-intervention: 73.0% Thus, we expect to be able to detect an absolute proportional difference of 10%.
Sample size/power calculation for NSQIP outcomes			
Readmissions	Pre- vs. Post-test proportion of patients readmitted	Pre-Intervention: 377 Post-intervention: 377	Proportion of Patients readmitted Pre-intervention: 23% Post-intervention: 15%

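### Pre/post results from the same residents are assigned unpaired tests, which have about 51% power for the 11-point change that Table 7 rates at 80%

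*SAP*

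**What the plan says.** The SAP section on within-group differences is headed as repeated measures. For dichotomous outcomes it says "Repeated measure differences on dichotomous outcomes will be examined using Chi-square" and Fisher's exact tests, plus logistic regression on resident factors. For ordinal outcomes, differences "between pre- and post-intervention testing will be examined using Chi-square tests, unadjusted ordered logistic regression" and an adjusted ordered logistic model. No McNemar test, conditional logistic regression, GEE, mixed model or clustered variance is mentioned.

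The within-group row of Table 7 gives the sample as "Pre-intervention: 160 Post-intervention: 160 (Repeated Measures" and rates of 50.0% before and 61.0% after, at 80% power and alpha 0.05. It concludes that "we expect to be able to detect a proportional absolute difference of 11% for within-group assessments". The 160 is the 200 residents expected per group less 20% loss. Table 7 gives no formula, sidedness, within-resident correlation or discordant proportion.

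For the patient outcomes, the SAP stresses that the pre and post samples are independent rather than repeated, yet it names the same chi-square and Fisher tests.

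**The concern.** Chi-square, Fisher's exact and standard logistic or ordered logistic models compare two separate groups. Here each resident contributes to both. If a resident's two results are positively correlated, the true variance of the pre/post difference is smaller than these tests assume. They then reject too rarely, and the gain from measuring the same person twice is lost.

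The power row is a separate problem. A minimum detectable difference describes a particular test, and the 11 points in Table 7 cannot be obtained from the tests the SAP names.

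The Protocol (Research Design and Methods) relies on within-group comparisons for two questions: the Delayed group's response to the curriculum at the end of year 2, and retention in the Early group. A test that is too conservative can miss a real gain in the first. In the second it can miss a real decline, and the null result could then be read as retention.

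**Working it through.** **Inputs.** From Table 7: p1 = 0.50, p2 = 0.61, d = 0.11, n = 160 at each time point, alpha 0.05, power 80%. Sidedness is not stated; two-sided is assumed (z = 1.960 and 0.8416). The within-resident correlation (phi) is not given and is varied.

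**1. Reproducing the 160.**

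- One-sample test against a fixed 50%: n = [(1.960·√(0.50·0.50) + 0.8416·√(0.61·0.39)) / 0.11]² = (1.3905 / 0.11)² = 159.8, so 160. This treats the pre-test rate as known.
- McNemar with discordant proportion D: n = [(1.960·√D + 0.8416·√(D − d²)) / d]². At D = 0.25, D − d² = 0.25 − 0.0121 = 0.2379 = 0.61·0.39, so the expression is identical and again gives 159.8. With these margins, D = 0.25 corresponds to phi of about 0.51.

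**2. The planned unpaired chi-square at 160 vs 160.**

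- Pooled rate (0.50 + 0.61)/2 = 0.555.
- Critical difference: 1.960·√(2·0.555·0.445/160) = 0.1089, or 10.9 points.
- Standard error under the alternative: √[(0.2500 + 0.2379)/160] = 0.0552.
- Power: Φ[(0.1100 − 0.1089)/0.0552] = 50.8%.
- Exact enumeration for independent samples gives 50.6% for chi-square and 46.1% for Fisher. One-sided alpha gives 63.2%.
- For 80% power: n = [1.960·√(2·0.555·0.445) + 0.8416·√(0.2500 + 0.2379)]² / 0.11² = 320 per time point. With 160 per time point, the detectable change is 50% to 65.4%, or 15.4 points.

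**3. Paired data.** With D = p1 + p2 − 2·p11 (p11 = proportion adequate both times):

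- McNemar power = Φ[(d·√160 − 1.960·√D)/√(D − d²)].
- True type I error of the unpaired test = 2·[1 − Φ(1.960/√(1 − phi))].

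| phi (assumed) | D | McNemar power | Unpaired chi-square power | Unpaired type I error |
|---|---|---|---|---|
| 0 | 0.500 | 50.3% | 50.8% | 5.0% |
| 0.2 | 0.403 | 59.4% | 50.9% | 2.8% |
| 0.3 | 0.354 | 65.0% | 51.0% | 1.9% |
| 0.4 | 0.305 | 71.6% | 51.0% | 1.1% |
| 0.5 | 0.256 | 79.1% | 51.1% | 0.6% |
| 0.6 | 0.207 | 87.1% | 51.3% | 0.2% |
| 0.7 | 0.159 | 94.5% | 51.5% | 0.03% |

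At round values of D, McNemar power is 80.1% (0.25), 65.5% (0.35), 54.6% (0.45) and 50.3% (0.50). The unpaired power barely moves with phi because 11 points lies almost exactly on the critical difference. Simulation of paired data gave 50% to 51% for phi from 0 to 0.6.

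**4. Cross-check.** The between-group row (159 per group, 50% vs 65.5%) reproduces with the unpaired formula: n = 159, power 80.2%. The mismatch is therefore confined to the repeated-measures row.

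**The case against.** - **Table 7 may rest on a sound paired calculation.** The row is labelled as repeated measures, and 160 is what McNemar gives at 25% discordance. This stands as far as it goes: 160 is not an arithmetic slip, and its origin can only be inferred. But the planned test is not McNemar and the discordance is not stated, so the claimed power belongs to an analysis that is not in the plan.
- **Chi-square might loosely mean McNemar's chi-square.** This is not credible. It is listed with Fisher's exact test, and the same pair is named for samples that the SAP calls independent.
- **Discordance could be below 25%.** True. At phi 0.6 or 0.7 a paired test would have 87% or 94% power, so 80% is not a ceiling. That argues for stating the assumption and specifying the paired test; the planned test stays near 51% throughout.
- **The error is conservative and does not touch the randomised contrast.** With positive correlation it does not create false positives, and Hypothesis 1 is a between-group comparison. This limits the damage, but the Delayed group's year-2 response and Early-group retention are still within-group questions.
- **The true effect may exceed 11 points.** The SAP cites a 20-25% increase from similar training. Read as absolute points from 50%, the planned chi-square has about 96% to over 99% power. Read as relative (60% to 62.5%), it has about 44% to 62%. The wording does not settle which, and the 11-point claim fails either way.
- **Site clustering is ignored.** It is, in every figure here and in Table 7. That is a separate matter and does not rescue the stated power.

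**Conclusion.** The concern holds, and the plan is wrong as written on two counts. Tests for independent samples are assigned to paired data, and the 80% power for an 11-point change is not that of the named test. That power is about 51% two-sided (63% one-sided, about 46% with Fisher), against 320 per time point needed for 80%. Under a correct paired test, 80% holds only if discordance is about 25% or lower (phi about 0.51 or higher); at 50% discordance it is 50%.

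These figures assume two-sided alpha unless marked, 160 complete pairs, and no clustering by site. The type I error figures also depend on the assumed correlation, which the documents do not give. The finding that the named tests ignore the pairing depends on none of these assumptions.

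**What to change.** In the within-group section of the SAP:

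- Test paired dichotomous outcomes with McNemar's test or conditional logistic regression. Conditional logistic regression removes time-fixed resident characteristics such as sex by design. If their coefficients are wanted, or residents with only one assessment are to be kept, use a logistic model with a random resident effect or GEE.
- Test paired ordinal outcomes with an ordinal mixed model (random resident effect) or the Wilcoxon signed-rank test.

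In Table 7, name the test and sidedness for the within-group row, state the assumed discordant proportion and its basis, and restate power or detectable difference over at least 25% to 50% discordance, with lower values if they can be supported. Note whether site clustering is included.

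The cost is SAP wording and one table row, with no added participants. The Protocol already uses a unique study ID on surveys and assessments, so pairs can be linked. The drawback is that the restated power falls below 80% unless discordance is about 25% or lower.
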